3. STUDY DESIGN

We will conduct a pragmatic two-arm, parallel groups 36-week multi-site randomized controlled single blind trial of SBIRT-PM. Drawing from VISN1 medical centers, we will randomize 1100 post-911 era Veterans applying for MSD-related compensation to either: 1) SBIRT-PM, a single phone-delivered session followed by up to three calls in a 12-week period and an additional call in the 12-32-week period; or 2) usual care (UC). Primary outcomes will be change in pain severity (BPI Composite severity) and change in the number of substances categorized as requiring intervention (ASSIST). The two primary outcomes will be measured by self-report at 12- and 36- week follow-ups. The self-report BPI and ASSIST measures will be completed with the Research Assistant by

telephone with the patient's responses entered directly into REDCap. The Research Assistant conducting all study assessments will be blinded. Secondary outcomes will include non-pharmacological pain management service utilization, pain interference with life activities (BPI), overall pain (PEG), overall health (EQ-5D-5L), use severity for individual substances generated by the ASSIST, and toxicology results for individual substances. The trial will include cost-effectiveness and budget impact analyses.

Study Settings.

The study will occur within the eight VISN1 VA medical centers (VAMC) located across six New England States. Each site provides MSD-related compensation examinations, addiction/mental health treatment, and a variety of non-pharmacological pain treatments.

The medical centers are:

1. Bedford VAMC
2. Boston Healthcare System
3. Central Western Massachusetts
4. Connecticut Healthcare System
5. Maine Healthcare System
6. Manchester VAMC
7. Providence VAMC
8. White River Junction VA

Feasibility of Recruiting a Sufficient Number of Veterans Who Meet Inclusion/Exclusion Criteria:

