9.2 Sample Size and Randomization

Given there are two primary outcomes (change in pain severity from the BPI, change in the number of substances whose use requires intervention based on the ASSIST), Bonferroni correction was used to generate a p-value of .025 for the sample size calculations for each outcome.

The planned (randomized) sample size is 1100 with sample selection at each site proportional to the size of the site. This sample size was based on power=.90 using alpha=.025, and an expected ES of $d=.25$ for pain severity. Breakdown as follows: 400 per group divided by '1 – loss to follow-up' (73%) = $548 \times 2 \text{ groups} = 1096$. Clustering was removed from the calculation per the advice of the PMC3 Biostatistics workgroup leadership during our protocol review. Instead, site will be controlled in analyses and a site by treatment interaction effect tested. In addition, power was increased to 90% based on their advice.

The planned sample size allows for 27% attrition. Values are based on previous related work and our 12-week pilot study. In Poisson modeling of our pilot data, SBIRT was associated with a baseline-adjusted relative rate of pain-related appointments attended (a proposed mediator of SBIRT-PM) of RR (Exp(B))=1.6.

For substance use, the proportion converting to low risk on at least one substance in the treatment group was estimated as 27% and in UC as 10%. Attrition was set at 27%. For 90% power (alpha=.025), the calculations resulted in sample size of 128 per group divided by '1 – loss to follow-up' (73%) = $176 \times 2 \text{ groups} = 352$ as the total sample size. Given the sample size required for the pain outcome, a small effect size (absolute value of 6% between groups) would be detectable for the substance use outcome with 90% power. In the UG3 pilot study, 67% of the participants at baseline self-reported on the ASSIST a level of risky substance use (either alcohol, tobacco or other drugs) that would require intervention and 33% reported risky alcohol use. Projected to the full trial, this suggests 737 participants are likely to have a clinically significant problem with at least one substance and 357 will have a problem with

alcohol. Thus, we will have an adequate sample in the UH3 RCT to detect changes in our primary substance use outcome.

Treatment Assignment Procedures

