9.6 Data Analyses

All variables (Intervention, covariates and outcomes) will be described with the use of the approximate summary statistics (mean, median, interquartile range, and percent). Multivariate models will be used following the examination of bivariate tests of outcomes by intervention group. A successful outcome will be either a reduction in pain severity or number of substance use above the “no intervention” threshold in the ASSIST or toxicological analysis of nail clippings. The model type will be selected based on meeting of modeling assumptions including the outcome distribution; Potential models will include linear and non-linear mixed-effects (Poisson (with over-dispersion), negative binomial, binary outcome) regression modeling. If there is a large skew with many zeros (which is quite possible where the outcome is change in the number of substances no longer needing intervention), we will use a negative binomial. If the distribution is a combination of 0's (no change) and 1's (change to level of “no need for intervention” in one substance) with very few outcomes greater than 1, a binomial distribution will likely be used. A Poisson model will be used if there are very few successes and they have a Poisson distribution.

These common rules will be used for guidance:

- Poisson distribution, if mean = variance
- Binomial distribution, if mean > variance
- Negative binomial distribution, if mean < variance

The covariance structures will be explored to determine which (unstructured, compound symmetry, autoregressive) is the most appropriate in mixed models. Selection will be based on the lowest AIC. An intervention by time interaction will be tested in the models – this will show the effect of the intervention on the outcome compared to controls.

Change in Pain: We anticipate using linear mixed-effects modeling to test the effect of SBIRT-PM on the 12-week value of the BPI, if it is a normally distributed outcome. We will in addition test simultaneously the unique effects of treatment on pain outcomes at week 12 and week 36, controlling for baseline differences, and test the equality of these parameters using the Wald test.

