Change in Substance Use: We anticipate using non-linear mixed-effects (Poisson, negative binomial, binary outcome as discussed above) regression modeling to test the effect of SBIRT-PM on the number of substances requiring intervention (according to the ASSIST), a count outcome. One subset of analyses will use risk sets

(at least 1 substance at baseline, at least 2 substances at baseline, etc.) to analyze substance risk changes in substance users. We will also test the equality of treatment effects at weeks 12 and 36 as described above.

We have identified stratification variables to account for error variance as a recommended good practice. Key covariates to be included in the model are depression, TBI, and mental health diagnoses (grouped into multiple more homogenous groupings, such as mood and psychotic disorders) as these are highly related to pain perception and substance abuse as well as the urn covariates—namely sex, race, ethnicity, self-reported illicit drug use and site. The strata used for the urn randomization are only to better ensure balance on key characteristics. Their main effects will not be interpreted in the analysis, though they will be examined as potential modifiers of the intervention effect. We will also consider as potential covariates: distance to nearest VA medical center, number of pain treatment modalities used at baseline, reasons patient might drop out of the study, and the probability of withdrawal. Opioid-use will be examined as a mediator as well as a tertiary outcome. Actual participation in SBIRT-PM (Y/N) will be examined as a mediator of response.

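### The substance-use co-primary is defined as a count, but the model-selection rule and the sample size are written for an improvement-only outcome, so the stated 90% power is not power for the co-primary

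*Combined protocol and SAP*

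**What the plan says.** Three places name the count. Section 1.1 (Objective 2) aims to reduce the number of substances needing any intervention. Section 9.5.1 gives the primary outcome as the number above the no-intervention threshold on the ASSIST. The paragraph on change in substance use in Section 9.6 models "the number of substances requiring intervention (according to the ASSIST), a count outcome". Section 3 calls the outcome "change in the number of substances categorized as requiring intervention (ASSIST").

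The general rule earlier in Section 9.6 reads differently. It expects a skewed distribution with many zeros "where the outcome is change in the number of substances no longer needing intervention". It then describes zeros as no change, ones as a single substance moving out of need, and a Poisson model when successes are few. The substance-use paragraph takes up this rule by referring back to the binary option discussed above it.

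Section 9.2 sizes the outcome on a third wording: "the proportion converting to low risk on at least one substance in the treatment group was estimated as 27% and in UC as 10" per cent. It continues "For 90% power (alpha=.025"), and "the calculations resulted in sample size of 128 per group", which becomes 352 in total after 27% attrition. Section 9.5.1 later defends power by noting that 571 participants with risky use exceed those 352.

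**The concern.** A count of risky substances can go up as well as down. The improvement score in the model rule has places only for no change and improvement. A participant who moves from one risky substance to three has no stated value. Under the sizing measure, a participant who drops one substance and takes up another counts as a conversion, although the count is unchanged.

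This is one of two co-primaries, each tested at 0.025. The model type is to be chosen from the outcome distribution, so an analyst following the general rule and one following the substance-use paragraph could fit different variables in good faith. The only power calculation for this co-primary also describes a variable that the primary-outcome section does not define.

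**Working it through.** **Inputs.** From Section 9.2: alpha 0.025 ("Bonferroni correction was used to generate a p-value of .025 for the sample size calculations for each outcome"), power 90%, 27% vs 10%, attrition 27%, and 400 evaluable per group for the pain outcome. Sidedness is not stated. Two-sided is assumed because it reproduces the plan's figure; one-sided gives 108 per group.

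**Step 1: reproduce the plan's figure.** Mean proportion = 0.185, z(0.9875) = 2.2414, z(0.90) = 1.2816.

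n = [2.2414·√(2·0.185·0.815) + 1.2816·√(0.27·0.73 + 0.10·0.90)]² / 0.17²
= (1.2309 + 0.6867)² / 0.0289 = 127.2, so 128 per group.

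128/0.73 = 175.3, so 176 per group and 352 in total. The match is exact, and the variable sized is conversion of at least one substance.

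**Step 2: power for a variable that can also worsen.** As a simple stand-in for the count, let each participant's net change be −1 (improve, probability i), +1 (worsen, probability w) or 0. The mean is w − i and the variance is i + w − (w − i)². Power = Φ(difference / √((v1 + v0)/n) − 2.2414). This is a normal approximation without baseline adjustment, not the planned mixed model. Improvement is held at 27% vs 10%. The worsening rates are assumptions, because the documents give none.

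Worked case, 10% worsening in both arms:
- SBIRT-PM variance: 0.37 − 0.17² = 0.3411
- UC variance: 0.20 − 0² = 0.2000
- Difference in means: 0.17
- n = 128: 0.17/√(0.5411/128) = 2.615; Φ(0.373) = 65%
- n = 400: 0.17/√(0.5411/400) = 4.622; Φ(2.381) = 99%

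| Worsening, same in both arms (assumed) | Sum of variances | Net change, 128/arm | Net change, 400/arm | Conversion, 128/arm |
|---|---|---|---|---|
| 0% | 0.2871 | 91% | >99% | 90% |
| 5% | 0.4191 | 77% | >99% | 90% |
| 10% | 0.5411 | 65% | 99% | 90% |
| 20% | 0.7551 | 49% | 95% | 90% |

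With no worsening the two tests agree. With equal worsening the mean difference is unchanged, but the variance grows and the conversion test does not register it.

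**Step 3: who the 27% and 10% describe.** Section 9.2 does not say whether these are proportions of everyone or of those with risky use. The comparison of 571 with 352 suggests the latter. If so, with the pilot's 67% at risk, the rates among all randomised are 0.67 × 27% = 18.1% and 0.67 × 10% = 6.7%, a difference of 11.4 points. The same formula at 400 per arm then gives:
- 10% worsening in both arms: variances 0.2744 + 0.1659 = 0.4403; 0.1139/√(0.4403/400) = 3.433; Φ(1.192) = 88%
- 20% worsening in both arms: variances 0.3805 + 0.2493 = 0.6298; 0.1139/√(0.6298/400) = 2.870; Φ(0.629) = 74%

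**Step 4: the 571 argument.** 571 × 0.73/2 = 208 per arm gives about 99% power for 27% vs 10%. The defence holds for conversion among users. It does not address a count in all randomised participants.

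**The case against.** The strongest reply is that the outcome is defined. The objective, the primary-outcome section and the substance-use paragraph all name the number of substances requiring intervention. The phrase about substances no longer needing intervention is a parenthetical illustration in guidance on distributions, and the binomial model is only said to be likely. That stands: the count is the better-supported reading, and the needed correction is to bring the rule and the power basis into line with it.

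Four stronger readings are tempting and are not supported:

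- **Worsening is scored as no change.** The rule gives worsening no value at all; scoring it zero is an inference.
- **A change outcome cannot be fitted by Poisson or negative binomial models.** Change need not mean a difference score. Section 9.6 tests an intervention-by-time term, which estimates change from repeated non-negative counts.
- **The plan would hide harm or reverse the conclusion.** ASSIST severity and toxicology for individual substances are secondary outcomes (Section 9.5.2), so worsening could be seen there. Losing or reversing the result needs more new risky use under SBIRT-PM than under UC. For example, 20% vs 10% worsening cuts net-change power to 30% at 400 per arm, but nothing in the documents suggests such an excess.
- **Nearly half the sample is fixed at zero under an improvement score.** Subtracting 571 from 1100 gives 529 (48%), but Section 9.5.1 states neither a denominator nor a time point for 571. The pilot's 67% in Section 9.2 implies about 33% instead.

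**Conclusion.** The mismatch is in the text and does not depend on any assumption: the co-primary is a count, while the model rule and the sample size describe improvement only. The 90% power, the 352 and the comparison with 571 all belong to conversion.

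The size of the consequence is conditional. It is nil if nobody worsens. With improvement of 27% vs 10% in everyone and 10% worsening in both arms, 128 per arm gives about 65% power for net change, while 400 per arm gives 99%. The planned 1100 may therefore still be enough. If the 27% and 10% apply only to those with risky use, 400 per arm gives about 88% at 10% worsening and 74% at 20%. The documents do not settle which case applies, so they support saying that power for the count is unstated, not that it is inadequate.

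**What to change.** 1. In Section 9.6, state that the co-primary is the number of substances above the no-intervention threshold on the ASSIST, in all randomised participants, adjusted for the baseline count. Name the primary time point (week 12 or week 36), which is not stated for this outcome.
2. Rewrite the distribution rule for that count and remove the improvement wording. The substance-use paragraph should then refer only to the revised rule.
3. Make conversion to low risk a secondary outcome among those with at least one risky substance at baseline, and tabulate new risky use by arm beside it.
4. In Sections 9.2 and 9.5.1, label the 27% vs 10% calculation, the 352 and the comparison with 571 as applying to that secondary outcome.
5. Restate power for the count, giving the assumed improvement rates, their denominator and the worsening rate.

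The cost is wording and one recalculation. No new data or participants are needed, but the power statement for this co-primary will probably be less favourable.

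### Section 9.6 does not put the baseline outcome value in the first-named test of either co-primary, leaving open less efficient readings than a baseline-adjusted analysis

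*Combined protocol and SAP*

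**What the plan says.** Section 9.6 (Data Analyses) brings in covariates in two steps. It says "Key covariates to be included in the model are depression, TBI, and mental health diagnoses", together with the urn factors (sex, race, ethnicity, self-reported illicit drug use and site). It then lists others to be considered, such as distance to a VA medical center and the number of pain modalities used at baseline. Baseline BPI severity and the baseline number of ASSIST substances above threshold are in neither list.

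For pain, the plan anticipates a linear mixed model to "test the effect of SBIRT-PM on the 12-week value of the BPI, if it is a normally distributed outcome". That sentence has no baseline term. A further model, introduced as an addition, estimates the week 12 and week 36 effects together and does adjust for baseline differences, but does not say in what form.

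For substance use, the plan anticipates a non-linear mixed model "to test the effect of SBIRT-PM on the number of substances requiring intervention", again with no baseline term. Comparison of the week 12 and week 36 effects refers back to the pain description. Risk sets defined by the baseline count are used in one subset of analyses.

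Section 9.6 also says that an intervention-by-time interaction will be tested, without saying whether baseline is one of the time points. The Précis, Section 3 and Section 9.2 call both co-primaries change.

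**The concern.** The baseline value of an outcome is usually among the strongest predictors of its follow-up value. The text fits at least three estimators: the week 12 value alone, a change contrast (by subtraction, or by an arm-by-time term with baseline as an unconstrained response), and a baseline-adjusted contrast. They differ in precision, and Section 9.6 does not choose between them for the first-named tests. I take those tests as primary because the joint model is presented as additional.

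At stake is the width of the intervals on both co-primaries, and whether chance baseline imbalance is removed from the estimate. The choice would also be left to a statistician who is not blinded (Section 6.2.3), in a plan that selects model type after looking at the outcome distribution.

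**Working it through.** **Inputs from Section 9.2.** "Bonferroni correction was used to generate a p-value of .025" for each outcome; "power=.90 using alpha=.025, and an expected ES of $d=.25$ for pain severity"; "400 per group divided by" the retained fraction; "The planned sample size allows for 27% attrition". The plan does not state sidedness, an SD, or the baseline-to-follow-up correlation r.

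**Reproducing the plan's sizes.**
- Pain: n per arm = 2(z₀.₉₈₇₅ + z₀.₉₀)²/d² = 2(2.241 + 1.282)²/0.25² ≈ 398 (398.4 with the t distribution), against 400 stated. Dropout: 400/0.73 = 548 per arm, 1096 in total, exact. A one-sided .025 test would need only 337, so two-sided is inferred.
- ASSIST outcome: "the proportion converting to low risk on at least one substance in the treatment group was estimated as 27% and in UC as 10" percent gives 128 per arm without continuity correction; 128/0.73 = 176 per arm, 352 in total, exact.

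The planned sizes therefore stand, and the pain calculation uses no baseline information.

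**Relative variance of the arm contrast (linear model, equal SDs at baseline and follow-up).**
- Week 12 only: 1
- Change, or unconstrained arm-by-time: 2(1−r)
- Baseline as covariate, or baseline-constrained longitudinal model: 1−r²

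Since 1−r² = (1−r)(1+r), the adjusted variance is never above 1, and it is (1+r)/2 times the change variance.

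**Power for BPI at 400 per arm, d=.25 on the raw follow-up SD, two-sided .025, no other covariates.** Power = Φ(0.25/√(2v/400) − 2.241) = Φ(3.536/√v − 2.241), where v is the relative variance.

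| Assumed r | Week 12 only | Change | Baseline-adjusted |
|---|---|---|---|
| .3 | 90.2% (v=1) | 77.2% (v=1.40) | 92.9% (v=.91) |
| .5 | 90.2% (v=1) | 90.2% (v=1.00) | 96.7% (v=.75) |
| .7 | 90.2% (v=1) | 99.0% (v=.60) | 99.7% (v=.51) |

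**If d=.25 is on the change SD instead.** The change test has 90.2% power at any r. The adjusted test, with v = (1+r)/2 relative to change, has 98.4% (r=.3, v=.65), 96.7% (r=.5, v=.75) and 94.4% (r=.7, v=.85).

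**ASSIST.** The documents give no count distribution and no correlation, and 1−r² is a linear-model result that does not carry over directly to a Poisson, negative binomial or binary model. I give no figure.

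**The case against.** The strongest reply is that baseline is already in the plan. Both co-primaries are called change, the pain paragraph is headed as change, and the mixed model comes with a choice of covariance structures and an intervention-by-time term, which fits poorly with an analysis of week 12 alone. The joint model adjusts for baseline explicitly, the ASSIST text points back to it, and a list of key covariates is not a full model specification. This stands to the extent that one cannot say both tests will lose precision. It does not settle the form of the baseline term: the explicit adjustment belongs to the additional model, and an unconstrained arm-by-time contrast is itself a change contrast, less efficient than adjustment at any r below 1.

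Three limits on the size also stand. The 77.2% figure needs d=.25 to be on the raw SD; on the change SD that shortfall disappears. The entry rule of BPI severity of at least 4 (Section 4.1) narrows the baseline range and may lower r, which shrinks the gain over week 12 alone. The covariates already planned may capture part of what the baseline value would explain, so the increment over the planned model is probably smaller than the table shows.

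For ASSIST, an outcome coded as conversion to low risk uses baseline status by construction, and the risk sets use it too. But the main model is on the count, the risk sets are one subset, and the illicit-drug urn factor covers neither alcohol nor tobacco, both of which count toward the 67% with risky use in the pilot (Section 9.2).

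**Conclusion.** The omission is real: neither first-named test has a stated baseline outcome term. Two plausible readings, week 12 only and unconstrained change, are less efficient than a baseline-adjusted analysis. For BPI, adjustment has the highest power at each assumed r in the table. The gain over week 12 alone runs from 90.2% to 92.9% at r=.3 up to 90.2% to 99.7% at r=.7. These figures rest on an assumed r, d on the raw SD, equal SDs and no other covariates.

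A reader might infer more, and the documents do not support it:
- That both tests certainly give away precision. If a baseline-adjusted or baseline-constrained model is already intended, the gain is zero.
- That the trial is undersized. The stated sizes reproduce, and the week 12 reading keeps the planned 90%. Power falls below plan only under the change reading, with d on the raw SD and r below .5.
- That the estimates would be biased. Randomization protects either test with complete data.
- That a percentage gain can be quoted for ASSIST. It cannot.

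This is an improvement worth making, not a flaw in validity.

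**What to change.** In Section 9.6, name baseline BPI severity (continuous) as a covariate in the pain models and the baseline count of substances above threshold as a covariate in the ASSIST models. Apply this to both the 12-week test and the joint week 12/36 model. A longitudinal model with baseline means constrained equal across arms is an acceptable alternative. State that the reported effect is the baseline-adjusted arm contrast at the named visit, and align the intervention-by-time sentence with that.

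The cost is a sentence or two. Both instruments are scheduled at baseline (Sections 6.1 and 9.5.1), and the intent-to-treat population is limited to participants who completed the baseline assessment (Section 9.3), so no new data and no change in sample size are needed.
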